Improving Outcomes for Emergency Department Patients with Alcohol Problems

NCT03536546

November 18, 2021

SPECIFIC AIMS

Reducing alcohol problems among Veterans is both a national priority and a priority research area for the Veterans Health Administration (VHA).¹ Hazardous use of alcohol is a linchpin at the core of post-deployment health. It is directly related to high volume and high morbidity problems in Veterans, including PTSD, suicidality and homelessness. This is particularly evident among Veterans from the recent wars, a cohort that has historically higher levels of hazardous alcohol use and concomitant mental health problems. Over the last decade, the VHA has undertaken several initiatives that have the potential to either directly or indirectly impact Veterans at risk for alcohol problems, including: 1) the rollout of universal alcohol screening in primary care, and the expansion of primary care-based alcohol brief intervention (BI) training; (2) the expansion of Emergency Department (ED) services which provide 24/7 access to care, and are frequently used by Veterans who have alcohol and mental health concerns; and, (3) the hiring of over 1,100 peer support specialists into mental health services to facilitate engagement with care and provide social support to Veterans with substance- and mental health-related problems.

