Alcohol Brief Advice Content. Participants who are randomized to either condition (APM or BA) will receive a modified BI (brief personalized advice guided by a script, a short pamphlet on alcohol, other health issues, and VHA contact information, and an infographic sheet about VA drinking guidelines as an additional layer of advice). In the APM condition, the brief advice session will be followed by 6 sessions of peer mentoring over 2 months. The BA condition includes the initial brief personalized advice and pamphlet. Materials for the APM and BA sessions will be provided in the ED. Participants may have the option to complete the session in-person or on the phone up to two-weeks after enrollment. The proposed brief advice for both the APM and BA groups will be short and personalized, based on factors such as gender, and severity of hazardous/harmful drinking.⁵⁰ The alcohol brief advice pamphlet to be given to the participants will provide information on alcohol and resources available at the VHA and in the community, with places for the peer to add tailored content (e.g. alcohol issue; reasons for use, strengths to help with change; plans for change, etc.) to: 1) enhance the Veteran's cognitive preconditions for message processing or acceptance (receptivity); and 2) enhance message impact (salience) by selectively modifying behavioral determinants of desired outcomes. Tailoring allows broad topics to be narrowed to participant experience for relevance in a short time period. The APM intervention includes the peer establishing an ongoing relationship with the patient to share their story, and schedule a time for the first Post-ED 'booster'.

6-session Peer Mentorship. Peer mentors will provide structured booster support to Veterans who have been assigned to the intervention condition. The peer mentor will work with each participant in the APM condition over a 2-month period to discuss strategies for reducing hazardous drinking, support behavior change and encourage linkage to care. Peer mentors will address participants' goals and will provide emotional, informational, and appraisal support designed to help Veteran engage in primary and specialty care, as needed. Cases will be reviewed on a weekly basis by the project supervisor and one of the clinical investigators ([name] and [name]). Training will be manualized, peers will receive weekly supervision, and post-ED sessions will be audiotaped.

Table 1: Overview of Peer Mentor Post-ED Visits

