6: Plannin g for the Future	
 Solicit Veteran's issues and questions since last contact Encourage decreased alcohol use with strategies Review coping, social support and leisure options Review solutions to barriers and service options Encourage contact with primary and/or specialty care Summarize progress and plans

current usual practices of ED-based brief interventions and current staffing models. One-session brief clinician advice by a social worker in the ED has had mixed and modest positive effects, but it remains the cornerstone of most alcohol brief interventions in large health systems. Thus, the comparator will be real-world relevant, potentially helpful yet also conservative in terms of the extent to which it can influence longer-term drinking outcomes.

Peer Mentor Hiring, Training, and Supervision. Peer mentors will be hired according to current policy guidelines provided by the VHA Office of Peer Support Services. As is standard practice in VHA programs, we will not require the peer specialist to be matched with study patients on specific demographic characteristics (e.g. military service era, gender) because these requirements introduce practical and ethical hiring challenges and are unlikely to be upheld if the program is implemented across VA facilities with existing peer specialists. However, preference will be given to peer specialist applicants with experience with hazardous drinking/substance use disorders.⁵⁷ Peer specialists will complete standardized VA peer support training and certification through a training program approved by the Office of Peer Support Services. An example training

Peer Mentor Content. Peer mentors will deliver the brief advice in the ED and will initiate conversations with the patient for up to 6-sessions over 2 months post-ED visit. Strengths-based discussions will include a combination of scripted and open-ended content to best facilitate reductions in drinking and engagement across severity (see Table 1). All sessions will be audiotaped and will emphasize strengths and goals, focusing on reducing/stopping alcohol use and linkage to care and barriers (e.g., transportation, going with the Veteran to the first appointment, housing, job or family issues, etc.).

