Initial training will be conducted over 5-days and include: a) review of hazardous alcohol use and AUDs in the military and in the VHA, signs and symptoms, risks, and common comorbid conditions; b) delivery of the BI; c) content of the structured linkage sessions; d.) an overview of the array of VHA programs and services that (including shadowing peer counselors in these programs), e) motivation for change, methods to support gains, and ways to foster linkage to care, and, f) presentations from key staff in programs, including the homeless, embedded MH, Veteran Centers, and substance abuse programs. Following recommended guidelines⁵⁷, training will also include site-specific information such as (1) documentation requirements and progress notes in the electronic medical record, (2) crisis recognition and procedures, (3) a review of Ann Arbor VA policies and procedures, and (4) facility emergency trainings. Ongoing training with the peer mentor supervisor, a licensed social worker, will include any additional resources needed throughout the project. Following VHA Psychosocial Rehabilitation and Recovery Peer Support Handbook, the peer supervisor will be a Licensed Independent Professional with clinical privileges at the AA VHA. After the initial 3-day training that includes didactic and experiential content (e.g. role playing), the peers will meet on a weekly basis with the peer mentor research supervisor for supervision to discuss cases, content, and troubleshoot each of the interventions and follow-up contacts. Supervision will also include discussions of peer identity and how to prevent peer drift, an undesirable shift from a recovery-oriented role toward a more medical treatment role.⁵⁹ Some of the supervision will be provided in group format to foster a fellowship and mutual support among peer mentors. The supervisor will be encouraged to engage in the VHA Peer Support Supervisors National monthly conference call and to join the VHA Peer Supervisors' email listserv where helpful information is shared between listserv participants.⁵⁷ Supervision will follow best practice guidelines as laid out by the Pillars of Peer Support Services Summit on Peer Specialist Supervision.⁶⁰ The Project Supervisor will provide day-to-day supervision and will report progress to the investigators in monthly meetings.

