Self-Report Healthcare Service Use. We will use the Treatment Services Review (TSR) to measure health services use, which has adequate reliability and validity.⁷⁰ We will also access VHA electronic health data, focusing on primary care; substance abuse treatment, and psychiatric treatment services (including mutual aid groups such as AA, receiving detox services, and other substance abuse care settings).

Health Care Utilization using Medical Records. In the last year of the study, a review of participants' medical records will be conducted to determine diagnoses, service use (i.e., ED visits, hospitalizations, primary and specialty care) for one year pre- and post-entry into the study. We will use these data to assess agreement with self-report service use, particularly VHA services, and seek to understand sources of discrepancy. Data will be accessed through CPRS, Corporate Data Warehouse (CDW), and the Joint Legacy Viewer (JLV).

Health Functioning. One item from the SF-12⁷¹ will assess perceived health functioning, which are accepted

Table 2: Study Measures	Instrument	When*	#Min
Primary Outcomes			
Alcohol Consumption	TLFB	B, 3,6,12	20
Secondary Outcomes			
Alcohol Consumption	AUDIT	S, 3, 6, 12	5
Alcohol Consequences	SIP	B, 3, 6, 12	5
Health Service Use	TSR/CPRS	B, 3,6, 12	10-15
Health Functioning	SF-12	S, 3,6,12	
Depressive Symptoms	PHQ-9	B, 3,6,12	
PTSD Symptoms	PC-PTSD-5	B, 3,6,12	
Substance Use	ASSIST	B, 3, 6, 12	
Opioid Misuse	COMM	B, 3, 6, 12	
Problem Severity	BAM	B, 3,6,12	
Individual Factors			
Demographics	SAOM	S/B	5-10
Motivation to Change/Readiness	Rulers	B, 3, 6, 12	
Self-Efficacy	Ruler	B, 3, 6, 12	
Social Factors			
Social Support	mMOS	B, 3, 6, 12	10
Peers Services	WAI-SR	3	
Intervention Interaction	Metric, Sentiment		0

*S=Screen; B=Baseline, 3-month, 6-month, 12-month follow-ups

Veterans.²⁹

Substance Use

Alcohol, Smoking, and Substance Involvement Screening Test (ASSIST) is a structured interview for alcohol, tobacco, cannabis, stimulants, sedatives and opioid use disorders in general medical settings. We will use a brief screening for tobacco use (ASSIST-LITE) and the full ASSIST version 3 to measure use of all other substances.

Opioid Misuse: a modified version of the Current Opioid Misuse Measure (COMM) will assess extent of opioid medication misuse.

Individual Factors

Demographics: Background characteristics assessed include: age, sex, marital status, education, employment, income, legal history, deployment history, etc.⁷⁷

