parameter estimates that account for missing data under the missing-at-random assumption.⁸⁹ We will look for non-random attrition, and if we find, for example, attrition rates to depend on a baseline covariate, we will include this covariate in the model. If we find attrition to depend on treatment use or ideation at prior assessments, we will utilize an appropriate pattern mixture model or multiply impute data based on an appropriate pattern mixture model assumptions based on the observed missing data pattern.⁸⁸

Aim 1: Determine the efficacy of the ED APM intervention compared to BA on TLFB drinking frequency reports at 3-, 6-, and 12-months post-baseline. **Hypothesis:** Veterans with hazardous drinking who are randomly assigned to APM will have significantly greater reductions in total TLFB drinking frequency reports, compared to those assigned to CBA.

Data Analysis for Aim 1: The primary purpose of Aim 1 is to examine the impact of the intervention on frequency of drinking per TLFB interview. This outcome will likely follow the assumptions required for linear regression model, but we will adjust the model type as needed. Assuming this is the case; we will use a linear mixed-effects model and estimate the treatment effect as the difference in the time-averaged TLFB frequencies over the year of follow-up. Because reduction in problem alcohol use is of primary interest, the analysis will model change-scores from baseline in the response variable as dependent variable, and the independent variables will include the baseline values of the response variable, time in months since randomization, and the treatment group indicator. The parameter estimate of the treatment group indicator will estimate the time-averaged treatment effect. *In a second model, we will include an interaction of time by treatment group indicator to formally test the possibility that the effect varies over time. Models will include a random effect for which specific peer/clinician a participant was assigned.*

Aim 2: Determine the impact of the APM intervention on linkage to primary and specialty alcohol treatment services care, mental health symptoms and functioning at 3-, 6-, and 12-months post-baseline, compared to BA. **Hypothesis:** Veterans with hazardous drinking who are randomly assigned to APM will be significantly more likely to engage in primary, specialty care, and other VHA supportive services and to have improvements in mental health symptoms and functioning.

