Data Analysis for Aim 2: The focus of Aim 2 is to study intervention effects on secondary outcome of frequency of primary care and mental health specialty care visits (as two separate outcomes) from the TSR, calculated as an average number of visits per month during each follow-up period. Similar to Aim 1, analyses will generally use a mixed effect model framework. As described above, initial analyses will examine the distribution of outcome measures over follow-up in order to select an appropriate model (e.g. Poisson regression or a related method for counts of visits). Our analysis strategy will parallel Aim 1 in terms of the independent variables, *random effect for peer/brief advice, focus on time-average treatment effects, and additional modeling of interactions of group and time.*

Secondary Aim will determine the mediators (e.g., motivation to change, self-efficacy, coping, social support) of the effect of the intervention and linkage on subsequent alcohol use and alcohol-related consequences. **Hypothesis:** The effect of randomization to APM compared to BA on the primary outcomes (i.e., alcohol consumption and consequences) will be mediated by differences between groups in motivation to change, self-efficacy, and perceived helpfulness of peer support.

Data Analysis for Secondary Aim: *In order to establish temporal ordering, we will examine whether level of the hypothesized mediators at 3 and 6 months post-baseline mediates the effect of random assignment on 6- and 12-month measures of the three primary outcomes of alcohol use behaviors.^{90,91} We will first determine the whether study condition is associated with the hypothesized mediators over the first six months of follow-up and check for a direct effect of the mediators at 3 and 6 months on alcohol use as measured at 6- and 12-months follow-up. We will estimate the indirect effect of the intervention on alcohol use through the mediators and conduct significance testing of this effect using macros created by Preacher and Hayes.⁹²*

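### The Aim 2 mental health visit count does not separate the study's own peer sessions, given in APM only, from onward care

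*Combined protocol and SAP*

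**What the plan says.** - **Outcome.** Data Analysis for Aim 2 takes the "frequency of primary care and mental health specialty care visits (as two separate outcomes) from the TSR". Each count is expressed as a monthly mean within its assessment interval. The Aim 2 hypothesis also reaches to other supportive VHA services.
- **Records.** Self-Report Healthcare Service Use adds VHA electronic data on primary care, "substance abuse treatment, and psychiatric treatment services", and counts mutual aid groups among these. Table 2 lists the source as TSR/CPRS.
- **APM.** Under Alcohol Brief Advice Content, "the brief advice session will be followed by 6 sessions of peer mentoring over 2 months". Under Peer Mentor Content, peers "will initiate conversations with the patient for up to 6-sessions over 2 months post-ED visit".
- **BA.** The Brief Advice Condition section gives this arm no sessions after the ED.
- **Peers and the record.** Peer training covers "documentation requirements and progress notes in the electronic medical record". The exclusion criteria screen out patients with recent peer services, by medical record and again by self-report.
- **Exclusion of study contacts.** None is stated for either source. The nearest rule, under General analytic approach, adjusts for other addictions treatment that the study did not initiate. That is a covariate rule and does not define the outcome.

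**The concern.** Linkage is what the peer sessions are meant to produce, so delivering them should not itself register as linkage. The sessions cover triggers, coping, problem solving and social support, and a Veteran could honestly describe them as counselling. The plan's own exclusion criteria treat peer contact as something that patients report and records show. Because BA has no such sessions, the error can run in one direction only.

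It is also hard to undo. The participant makes the classification during the interview, and follow-up staff are blind to condition, so they cannot readily ask whether a contact was a study session. At stake is the reading of a positive 3-month result on mental health care, and of any analysis that carries linkage forward, such as the mediation aim.

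**Working it through.** **Inputs**
- Power and Sample Size Calculations: 360 retained of 450 (180 per arm at 1:1), two-sided alpha 0.05, control mean 1 per follow-up period, detectable rate ratio 1.34 at 80% power.
- Sessions: 6 in APM over 2 months, 0 in BA. Even with the permitted delay of two weeks for the ED session, they are planned to finish before 3 months.
- Assumptions, not in the documents: the share *f* of attended sessions reported or coded as mental health visits; mean attendance *s* of 6 (all) or 3 (half); and that the 3-month TSR covers the whole 0-3 month period, as the outcome definition implies. The half value borrows the 50% attendance reported for the team's earlier case management. The plan does not say that this means half of the sessions.

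**1. The plan's own figure.** Poisson regression with a 1:1 binary covariate (Signorini formula):

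power = Φ{[√(N·λ₀)·ln RR − 1.96·√4] / √[2(1 + 1/RR)]}

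With N = 360, λ₀ = 1 and RR = 1.34: (18.97 × 0.2927 − 3.92) / 1.869 = 0.874, so power is 80.9% against the stated 80%. The figure reproduces.

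**2. Threshold at 3 months, no true effect.** With *x* = *s·f* miscounted sessions per APM participant and control mean *m*, the spurious ratio is 1 + *x/m*.
- *m* = 1: 1 + *x* = 1.34 gives *x* = 0.34, which is 0.34/6 = 5.7% of sessions if all six are attended, or 0.34/3 = 11.3% if three are.
- *m* from 0.5 to 3: *x* = 0.34*m*, so 0.17 to 1.02 sessions.

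**3. Threshold for the time-averaged effect.** Control mean 1 in each of three periods, equal weight, error in the first period only.
- Ratio of averages: (3 + *x*)/3 = 1.34 gives *x* = 1.02.
- Average log ratio: ln(1 + *x*)/3 = ln 1.34 gives *x* = 1.34³ − 1 = 1.41.
- As a share of sessions, the first is 17% of six or 34% of three.

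**4. What a given share would do at 3 months** (*m* = 1, 180 per arm, Wald test on the log rate ratio, no true effect)

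| Share counted | Attended | Spurious ratio | Chance of rejecting the null |
|---|---|---|---|
| 0% | any | 1.00 | 5% |
| 5% | 3 | 1.15 | 28% |
| 5% | 6 | 1.30 | 75% |
| 10% | 3 | 1.30 | 75% |
| 10% | 6 | 1.60 | 99.9% |

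At 10% counted, the ratio runs from 1.2 (*m* = 3) to 2.2 (*m* = 0.5) with six sessions attended, and from 1.1 to 1.6 with three.

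**The case against.** The best defence is that the named outcome is mental health *specialty* care. The plan treats peer mentoring as the route to such care, and supervision is meant to stop peers drifting into a treatment role. On a plain reading a peer session is not a specialty visit. The TSR wording is not in the documents, so how participants would classify a session is unknown. This stands as a limit on how likely the error is and how large. It does not fill the gap, because participants make the classification without a rule.

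Second, the Aim 2 count is said to come from the TSR, and records are not shown to feed it. A reader might infer from "the hiring of over 1,100 peer support specialists into mental health services" and the training in progress notes that study sessions will be logged as mental health encounters. The documents do not support that. The first describes a national hiring initiative and the second a training topic, while the study's peers work within the research team. The record risk applies only to record-based measures.

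Third, the planned comparison of self-report with records and the attendance data offer some check. Both help only in part. A session present in both sources would simply agree, and attendance shows how many sessions took place, not how many were reported as visits.

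Fourth, a blunt instruction to ignore all study contacts could make APM participants omit genuine visits that a peer attended with them, which Peer Mentor Content allows for. It could also prompt replies that unblind the interviewer. This is right, and the wording below is built around it.

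**Conclusion.** The omission is real, and any resulting error favours APM. It bears on the mental health specialty count and on any record-based or supportive-service measure. It is concentrated at 3 months and diluted in the time average; the primary care count is little exposed. A small share of miscounted sessions would be enough: 0.34 per APM participant at 3 months, or about 1.0 to 1.4 for the time average, reaches a ratio of 1.34 with no true effect. These are thresholds, not estimates. They rest on a control mean of 1 that the plan offers as an example for alcohol-related treatment visits, not for mental health visits.

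A reader might infer that Aim 2 will show spurious linkage, with a 3-month ratio of 4.0 at half attendance. That needs all three attended sessions to be miscounted, which nothing in the documents suggests. Nor do they say that the linkage effect is expected to peak at 3 months.

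Aim 2 is among the primary specific aims, but the plan classes service use as a secondary outcome, and the TLFB primary outcome is untouched. This is a cheap improvement that should be made, not a flaw that undermines the trial.

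**What to change.** 1. In Self-Report Healthcare Service Use and Data Analysis for Aim 2, define Aim 2 visits as excluding the ED brief advice session and the peer mentor sessions.
2. At each TSR (3, 6 and 12 months), read one identical instruction to both arms: *Do not count the advice session or any peer mentor sessions given by this study; do count every visit with any other provider, even if someone from the study arranged it or came with you; please do not tell me whether you had study sessions.*
3. Drop encounters by study peers or study staff from any record extract.
4. For 3-month interviews already done, report a bound: recompute each APM participant's mental health count as reported visits minus attended sessions, not below zero, and show it beside the unadjusted result. Report the 6- and 12-month effects separately.

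The cost is a sentence in the definition, a sentence in the interview and a filter in the extract; the sample size does not change. The downsides are slight under-reporting of non-study peer contacts and a small unblinding risk, which the last clause of the instruction limits.
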